**Table 4: Non-hematological Toxicities: Modifications for Various Expected Toxicities**

| Non-hematological Toxicity Dose Reductions for Conformal Radiotherapy |   |
|---|---|
| Event   | Action  |
| Nausea   |   |
| Grade 1-2   | None  |
| Grade 3   | Hold until resolved to $\leq$ Grade 2, then resume treatment. |
| Grade 4   | Hold until resolved to $\leq$ Grade 2, then resume treatment. |
| Vomiting   |   |
| Grade 1-2   | None  |
| Grade 3   | Hold until resolved to $\leq$ Grade 2, then resume treatment. |
| Grade 4   | Hold until resolved to $\leq$ Grade 2, then resume treatment. |
| Mucositis  |   |
| Grade 1-2   | None  |
| Grade 3   | Hold until resolved to $\leq$ Grade 2, then resume treatment. |
| Grade 4   | Hold until resolved to $\leq$ Grade 2, then resume treatment. |
| Esophagitis  |   |
| Grade 1-2   | None  |
| Grade 3   | Hold until resolved to $\leq$ Grade 2, then resume treatment. |
| Grade 4   | Hold until resolved to $\leq$ Grade 2, then resume treatment. |
| Fatigue  |   |
| Grade 1-2   | None  |
| Grade 3   | Hold until resolved to $\leq$ Grade 2, then resume treatment. |
| Grade 4   | Hold until resolved to $\leq$ Grade 2, then resume treatment. |
| Dermatitis   |   |
| Grade 1-2   | None  |
| Grade 3   | Hold until resolved to $\leq$ Grade 2, then resume treatment. |
| Grade 4   | Hold until resolved to $\leq$ Grade 2, then resume treatment. |

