#### **4.10 Expected Adverse Events**

Depending on the site of treatment, potential / expected treatment toxicities include Grade 1 to 3 toxicity of the following symptoms, with Grade 3 occurring in no more than the following percentages of patients:

|             |     |
|-------------|-----|
| Dermatitis  | 20% |
| Nausea      | 20% |
| Fatigue     | 20% |
| Vomiting    | 20% |
| Diarrhea    | 20% |
| Mucositis   | 20% |
| Esophagitis | 20% |

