### **Stopping Rules:**

The study will be suspended for a safety review if 5 or greater “Probable” or “Definite” Serious Adverse Events occur or greater than 5 unexpected toxicities of  $\geq$  Grade 3 occur.

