### **8.1.2 Unexpected Adverse Event**

An unexpected adverse event is any adverse treatment experience where the specificity or severity of which is not consistent with the applicable product information (e.g., Investigator's Brochure for an unapproved investigational product or package insert/summary of product characteristics for an approved product).

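### The suspension rule has no limb for non-serious, expected Grade 3 toxicity, so no numerical rule ever tests the 20% ceilings in Section 4.10

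*Combined protocol and SAP*

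**What the plan says.** The rule under Stopping Rules in Section 7.1 has two limbs. The first reads "The study will be suspended for a safety review if 5 or greater" and then names SAEs attributed Probable or Definite; it does not ask whether the event was expected. The second fires at "greater than 5 unexpected toxicities of" Grade 3 or higher, that is, at six or more. Neither limb gives a number of patients treated or says whether events or patients are counted.

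Section 8.1.2 calls an event unexpected when its specificity or severity "is not consistent with the applicable product information". The Investigator's Brochure and the package insert are given as examples. Section 4.10 is not mentioned there or in the rule.

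Section 4.10 lists dermatitis, nausea, fatigue, vomiting, diarrhea, mucositis and esophagitis as expected at Grades 1 to 3, "with Grade 3 occurring in no more than the following percentages of patients"; the percentage is 20% for all seven. Table 4 in Section 4.3, titled "Modifications for Various Expected Toxicities", has Grade 4 rows for six of these (diarrhea is absent).

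Section 7.3 reports the incidence of Grade 3 or higher toxicity and makes no comparison with the 20% figures. Section 9.2 has the DSMC review all adverse events, in aggregate every month, and the application of the study's stopping rules. It gives no numerical criterion of its own.

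**The concern.** Reporting toxicity is a primary objective (Section 2.1.4), and Section 4.10 sets an upper limit for each of seven Grade 3 toxicities. A reader would expect the safety rule to act when such a limit is passed. It does so only indirectly, through events that are also serious and attributed Probable or Definite. A listed toxicity could run well above 20% without meeting any prespecified criterion, and whether anyone acted would rest on judgement at the monthly review.

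Two drafting gaps add to this. Whether a Grade 4 event of a listed toxicity counts in the second limb depends on whether Section 4.10 or Table 4 is read as the expected list. And a raw count of five means something quite different after 10 patients than after 30, so the rule is least sensitive early, when a review could protect the most patients.

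**Working it through.** The plan states no error rate, reference rate or operating characteristic for this rule, so there is no figure to reproduce. The following uses the rule as written.

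**Inputs from the plan.** Limb 1: at least 5 Probable/Definite SAEs. Limb 2: at least 6 unexpected toxicities of Grade 3 or higher (both Section 7.1). Ceiling: 20% for each of 7 toxicities at Grade 3 (Section 4.10). N = 30 (Section 7.1).

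**Assumptions.** At most one counted event per patient, patients independent. The share *s* of expected Grade 3 events that are SAEs attributed Probable or Definite is not in the documents, so a range is shown.

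**Step 1: what each limb counts.** With Section 4.10 as the expected list:

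| Event | Limb 1 | Limb 2 |
|---|---|---|
| Listed toxicity, Grade 3, not serious | no | no |
| Listed toxicity, Grade 3, SAE, Possible or lower | no | no |
| Listed toxicity, Grade 3, SAE, Probable/Definite | yes | no |
| Listed toxicity, Grade 4 | only if a Probable/Definite SAE | yes by Section 4.10; no if Table 4 defines expected (diarrhea excepted) |

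The first row contributes nothing at any frequency.

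**Step 2: how well limb 1 stands in for the missing limb.** Take one toxicity at a true 40%, twice its ceiling. The number of qualifying patients is X ~ Binomial(30, 0.40·*s*), and limb 1 fires if X ≥ 5.

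| Assumed *s* | 0.40·*s* | P(X ≥ 5) |
|---|---|---|
| 0 | 0 | 0 |
| 10% | 0.04 | 0.006 |
| 20% | 0.08 | 0.087 |
| 30% | 0.12 | 0.288 |
| 50% | 0.20 | 0.745 |
| 100% | 0.40 | 0.998 |

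These are probabilities of firing at any time up to patient 30.

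**Step 3: the missing denominator.** Five events are 5/10 = 50% of 10 patients but 5/30 = 16.7% of 30; six are 60% and 20%. At a constant 20% rate of counted events per patient:

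| Patients treated | P(X ≥ 5) | P(X ≥ 6) |
|---|---|---|
| 10 | 0.033 | 0.006 |
| 20 | 0.370 | 0.196 |
| 30 | 0.745 | 0.573 |

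**Step 4: what a trigger on the ceilings would do.** For one toxicity, look after 10, 20 and 30 patients. At each look take the smallest count r with P(X ≥ r | n, 0.20) ≤ 0.05. This gives 5/10 (tail 0.033), 8/20 (0.032) and 11/30 (0.026). The probability of crossing at any of the three looks, by exact recursion over the looks, is:

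| True Grade 3 or higher rate | P(cross) |
|---|---|
| 20% | 0.062 |
| 30% | 0.357 |
| 40% | 0.764 |
| 50% | 0.962 |

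If all seven toxicities sit exactly at 20% and are independent, at least one crosses with probability 1 − (1 − 0.062)^7 ≈ 0.36. The 5% level and the look times are illustrative choices.

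**The case against.** The strongest reply is that the suspension rule is not the only safety review. The DSMC sees all adverse events monthly (Section 9.2), the investigator reviews all patient data at least monthly (Section 9.1), and serious or unexpected events go to the DSMC and IRB within 7 days (Section 8.3). Section 8.4 sets 15- or 30-day reporting deadlines for Grade 3 events, and Tables 3 and 4 act on Grade 3 in the individual patient. This stands. A reader might infer that an excess of expected toxicity, or a run of related SAEs in the first few patients, would pass without review; the documents do not support that. What is missing is a numerical criterion.

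A reader might also infer that the rule is blind to expected toxicity altogether. It is not. Limb 1 has no expectedness filter, so a listed toxicity that leads to hospitalization and is attributed Probable or Definite counts; if half of the events qualify, limb 1 fires with probability 0.745 in Step 2. Nor does the gap clearly reach Grade 4, since Section 4.10 stops at Grade 3.

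A third inference is that unexpectedness cannot be defined for radiotherapy. Section 8.1.2 gives its reference documents only as examples, and Section 4.10 is a natural list to use. The defect is the missing cross-reference and the conflict with Table 4.

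Finally, with N fixed at 30 a raw count works as a crude end-of-study limit (16.7% or 20%). That is fair, but it offers little while few patients have been treated.

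**Conclusion.** The concern holds in this form. With Section 4.10 as the expected list, non-serious Grade 3 events of the seven toxicities count in neither limb, and no numerical rule or planned analysis compares any of them with its 20% ceiling. How far the SAE limb makes up for this depends on a share the documents do not give: at twice the ceiling, its chance of firing runs from 0 to 0.998 as that share goes from 0 to 100%, and is below 0.30 while the share is 30% or less. The reference for unexpectedness, the status of Grade 4 and the counting unit are open to more than one reading. This weakens a safeguard that sits alongside working DSMC oversight; it does not leave the trial unmonitored. The probabilities assume independent patients with at most one counted event each.

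**What to change.** 1. Reconcile Section 4.10 with Table 4 on Grade 4. Then define expectedness in Sections 7.1 and 8.1.2 by reference to the reconciled list.
2. State in Section 7.1 that patients are counted, and report each count with the number treated so far.
3. Add one DSMC review trigger (a review, not automatic suspension) for each listed toxicity. It applies when the number of patients with Grade 3 or higher crosses a prespecified exact-binomial boundary against the Section 4.10 ceiling. The boundary should cover all 30 patients, and its cumulative false-alarm rate should be stated both per toxicity and across the seven. The boundaries 5/10, 8/20 and 11/30 are one illustration; a stricter level would lower the 0.36 chance of at least one false alarm across the seven, at the price of slower detection.

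The cost is a protocol wording change, a running tally for the monthly DSMC meeting, and an occasional extra safety review. The data are already being collected.

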## **7.2 Sample Size and Accrual**

We performed calculations to detect a change in patients’ BPI pain scores before and after treatment using the Wilcoxon signed-rank test. Using the software G\*Power 3.1.2 (University Kiel, Germany) the following calculations were made. To detect a mean change of 2 units on the BPI scale with a standard deviation of 3, and achieve a 2-sided alpha of 0.05 with 80% power, a sample size of 21 is needed. Most studies report a mean improvement in pain scores of about 3.5. (32). Thus we anticipate an improvement by at least 3 on the BPI in our study, which should be adequately powered with 30 patients.

Since we have had accrual from prior studies of about 20 patients a year and this is a pilot study, we thought that a sample size of 30 subjects would be realistic for accrual and provide the necessary patient data for optimization of the software systems. We treat approximately 30 patients with osseous metastases annually at UVA with palliative radiotherapy. We anticipate an accrual rate of 20 cases per year over 18 months. Since the power analysis requires a sample size of

21, accrual of 30 subjects would allow for dropouts and still have sufficient power.

### **7.3 Data Analyses Plans**

Treatment response as defined by International Bone Metastases Consensus Group will be determined for each patient. As described in Section 6.1.1, pain intensity as defined by the BPI and opiate use as quantified by the OMED will be used to categorize patients as having: Complete Response, Partial Response, Pain Progression, Stable Pain. At each evaluation, the patient's BPI and OMED at that visit will be compared to the pre-treatment levels. The "Worst Pain" score from the patient's BPI will be used to evaluate for treatment response. Patient response does not require a statistical analysis. The percentage of patients in each response category at each evaluation will be reported.

Patient pain will be recorded using the BPI before treatment and at designated evaluations after treatment. Pain scores before and after treatment will be compared using a Wilcoxon signed ranks test to determine if there is a statistically significant difference. Example: Pre-treatment vs. 1 week, Pre-treatment vs. 4 weeks, etc.

Analgesic use will be recorded by requiring each patient to keep a logbook of their analgesic intake. Their opiate intake for the last 72 hours will be converted to OMED at each evaluation and used in the categorization of treatment response. The difference between their OMED before and after treatment will be compared using paired two-sample t-tests.

Patients' functional status will be determined using the Karnofsky Performance Scale at each evaluation. The difference between the KPS before and after treatment will be compared using a Wilcoxon signed ranks test.

Patients' quality of life will be measured using FACT-BP and FACT-G scores at each evaluation. The difference between the FACT scores before and after treatment will be compared using a Wilcoxon signed ranks test.

Patient satisfaction will be measured using a modified version of FACT - TS – BTCSQ. No statistical analysis will be required for reporting the results. The average scores from the satisfaction survey will be reported.

To evaluate the CT detector dose calculations, the delivered radiation dose obtained using the phantom quality assurance will be compared to the exit radiation dose quality assurance calculation. The calculated dose and delivered dose for each patient will be compared using a paired two-sample t-test, and the % difference in dose will be reported.

Contours generated from the conventional and experimental image registration flows will be compared in a variety of ways as described in Section 7.1. All comparisons of the contouring measures, including the Dice indices, will be performed using paired two-sample t-tests.

Toxicity will be recorded using CTCAE 4.0 criteria and RTOG Late Radiation Morbidity Scoring Criteria. The incidences of grade 3 or more toxicities will be reported.

The effectiveness of the infrared tracking system will be determined by comparing its position calculations with the position of the patient as determined by the position of the lasers with respect to the set up skin marks before and after treatment. The position changes calculated by each method will be compared using paired two-sample t-tests.

The average treatment planning speed of radiation treatment planning with our current clinical system will be calculated and compared the average speed of planning with newer in-development algorithms running on next generation computers with graphic processing units. These means will be compared with two-sample t-tests.

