## **STUDY OVERVIEW**

- Eligible patients with 1-3 painful osseous metastases will receive a consultation and subsequently undergo CT simulation, radiation treatment planning, and their first radiation treatment on day 1.
- Patients will receive a total of 2-5 fractions of high dose palliative radiation therapy via helical TomoTherapy consisting of 5-10 Gray (Gy) per fraction with a minimum biologic effective dose (BED) of 25 Gy.
- Standard patient-specific treatment planning quality assurance will be performed on a cylindrical phantom with ion chamber and film measurement.
- Software provided by TomoTherapy Inc.® will be used to measure the radiation exiting the patient and recalculate the dose the patient received. This calculated dose will then be compared to phantom measurements and treatment planning calculations to validate the ability of this novel radiation dose verification software to verify the accurate delivery of radiation. This will not replace standard quality assurance measurements.
- At the Emily Couric Cancer Center, an in-house developed infrared motion tracking system will monitor patients' positions for any deviation from the treatment position. This is not standard of care but may augment standard safety measures with full implementation in the future and does not subject the patient to any risks or discomfort. Infrared motion tracking is will be optional and not required for patients treated at CRH.
- Contouring (the demarcation of the tumor and critical structures) will be performed in the standard manner for treatment planning.
- Contouring will also be performed in an expedited, experimental manner on diagnostic image sets which will then be compared to the standard contours. Experimental contouring will not replace standard contouring, nor affect treatment planning.
- Patients will complete questionnaires to capture pain scores of the treated lesion(s), analgesic use, patient functional status, patient quality of life, and patient satisfaction at 1 week, 4 weeks, 8 weeks, 12 weeks, 6 months, and 12 months following treatment. These scores will be compared to questionnaires completed pretreatment.
- Radiation-induced toxicities will be captured during treatment physical examinations and at follow-up physical examinations at 4 weeks, 12 weeks, 6 months, and 12 months.

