## **2.0 STUDY OBJECTIVES**

### **2.1 Primary Objectives**

Our primary objectives are to quantify outcomes of patients with osseous metastases treated via the STAT RT workflow. Specifically, we are plan to:

- 2.1.1** Estimate the response to palliative radiation as defined by International Bone Metastases Consensus Group using the BPI and OMED to categorize into Complete Response, Partial Response, Pain Progression, and Stable Pain after receiving treatment via the STAT RT workflow.
- 2.1.2** Estimate the change in the patient's quality of life and function as scored by FACT-BP and KPS after receiving treatment via the STAT RT workflow.
- 2.1.3** Estimate patient satisfaction with the STAT RT workflow using a modified FACIT-TS-BTCSQ survey.
- 2.1.4** Report the treatment-related toxicity using CTCAE Version 4 and RTOG Late Radiation Morbidity Scoring Criteria after receiving treatment via the STAT RT workflow.

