## **3.0 PATIENT ELIGIBILITY**

### **3.1 Inclusion Criteria**

- 3.1.1** Patient has a biopsy proven diagnosis of cancer. The osseous metastatic lesions do not need to be biopsied.
- 3.1.2** Patients with multiple myeloma are eligible for the study.
- 3.1.3** Patient has 1-3 major painful osseous metastases (target lesions) from any primary cancer or unknown primary cancer.
- 3.1.4** Long bone target lesions must have a Mirels fracture score of  $\leq 7$  (See Appendix G).
- 3.1.5** Radiation oncologist determines that the patient is medically able to undergo palliative radiation therapy.
- 3.1.6** Patient has target lesions that are radiographically consistent with metastatic disease on CT, MR, or PET CT obtained within 8 weeks of treatment.
- 3.1.7** Persistent distinguishable pain associated with target sites to be treated.
- 3.1.8** Patient average BPI pain score for last 72 hours at specified location is  $\geq 3$  (0-10 scale)
- 3.1.9** Patients may have additional non-painful or minimally painful osseous metastases (if patient has pain from additional sites, the pain from the additional sites must be evaluated as being less intense by at least 2 points on the BPI compared to the site(s) treated)
- 3.1.10** The patient may have previously been treated with external beam radiation therapy to other body sites, but not to the target sites.
- 3.1.11** The patient may have previously or currently be undergoing chemotherapy or bisphosphonate therapy.

- 3.1.12** The patient will be able to understand English (or a medical interpreter for their native language must be available for all study visits).
- 3.1.13** 18 years of age or older.
- 3.1.14** Life expectancy > 12 weeks.
- 3.1.15** Able and willing to answer simple survey questionnaires.
- 3.1.16** Able and willing to keep a logbook of analgesic use (with or without assistance)
- 3.1.17** Willing to return to clinic at 4 weeks, 12 weeks, 6 months, and 12 months after treatment.
- 3.1.18** Signed study-specific informed consent form.
- 3.1.19** Women of childbearing potential and men must agree to use adequate contraception (hormonal or barrier method of birth control) prior to study entry and for the duration of study participation. Should a woman become pregnant or suspect she is pregnant while participating in this study, she should inform her treating physician immediately.

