## **6.0 EVALUATION CRITERIA**

### **6.1 Response to Palliative Radiotherapy**

#### **6.1.1 Response Criteria According to the International Bone Metastases Consensus Group**

Complete Response (CR): Pain reduction to zero AND OMED\* stable or reduced

Partial Response (PR): Pain reduction by two scores or more AND OMED\* stable or reduced.  
OR  
Stable pain AND OMED\* reduction by 25% or more

Pain Progression (PP): Pain increase by two scores or more AND OMED\* stable or increased.  
OR  
No change in pain AND OMED\* increased by 25% or more (or start of morphine use after the baseline or epidural pain treatment at follow-up)

Stable Pain (SP): Stable pain AND stable OMED\*

OMED = Oral Morphine Equivalent Dose

\* The total OMED intake over the most recent 72 hours will be calculated at each evaluation.

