#### Brief Pain Inventory (Short Form)

Date: \_\_\_\_\_ / \_\_\_\_\_ / \_\_\_\_\_ Time: \_\_\_\_\_  
Name: \_\_\_\_\_ Last \_\_\_\_\_ First \_\_\_\_\_ Middle Initial \_\_\_\_\_

1. Throughout our lives, most of us have had pain from time to time (such as minor headaches, sprains, and toothaches). Have you had pain other than these everyday kinds of pain today?

1. Yes      2. No

2. On the diagram, shade in the areas where you feel pain. Put an X on the area that hurts the most.

3. Please rate your pain by circling the one number that best describes your pain at its **worst** in the last 24 hours.

|         |   |   |   |   |   |   |   |   |   |                                |
|---------|---|---|---|---|---|---|---|---|---|--------------------------------|
| 0       | 1 | 2 | 3 | 4 | 5 | 6 | 7 | 8 | 9 | 10                             |
| No Pain |   |   |   |   |   |   |   |   |   | Pain as bad as you can imagine |

4. Please rate your pain by circling the one number that best describes your pain at its **least** in the last 24 hours.

|         |   |   |   |   |   |   |   |   |   |                                |
|---------|---|---|---|---|---|---|---|---|---|--------------------------------|
| 0       | 1 | 2 | 3 | 4 | 5 | 6 | 7 | 8 | 9 | 10                             |
| No Pain |   |   |   |   |   |   |   |   |   | Pain as bad as you can imagine |

5. Please rate your pain by circling the one number that best describes your pain on the **average**.

|         |   |   |   |   |   |   |   |   |   |                                |
|---------|---|---|---|---|---|---|---|---|---|--------------------------------|
| 0       | 1 | 2 | 3 | 4 | 5 | 6 | 7 | 8 | 9 | 10                             |
| No Pain |   |   |   |   |   |   |   |   |   | Pain as bad as you can imagine |

6. Please rate your pain by circling the one number that tells how much pain you have **right now**.

|         |   |   |   |   |   |   |   |   |   |                                |
|---------|---|---|---|---|---|---|---|---|---|--------------------------------|
| 0       | 1 | 2 | 3 | 4 | 5 | 6 | 7 | 8 | 9 | 10                             |
| No Pain |   |   |   |   |   |   |   |   |   | Pain as bad as you can imagine |

|  |     |     |     |     |     |     |     |     |     |      |                       |
|--|-----|-----|-----|-----|-----|-----|-----|-----|-----|------|-----------------------|

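### Response is scored from a BPI worst-pain item that names no site: Complete Response can only be understated, and the other categories can err in either direction

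*Combined protocol and SAP*

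**What the plan says.** Primary objective 2.1.1 reads: "Estimate the response to palliative radiation as defined by International Bone Metastases Consensus Group using the BPI and OMED". Section 7.3 compares each visit's BPI and oral morphine equivalent dose (OMED) with the pre-treatment values, states that "The 'Worst Pain' score from the patient's BPI will be used to evaluate for treatment response", and reports the percentage of patients in each category without a test.

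Item 3 of the form in Appendix H begins "Please rate your pain by circling the one number that best describes your pain at its" and asks for the worst pain in the last 24 hours; no site is named. Item 2 is a body diagram on which the patient shades every painful area and is told: "Put an X on the area that hurts the most". Section 6.1.1 defines the top category as "Complete Response (CR): Pain reduction to zero AND OMED" stable or reduced, and its pain criteria name no site either.

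Other sections are site-specific. The Study Overview says: "Patients will complete questionnaires to capture pain scores of the treated lesion(s". Criterion 3.1.7 requires distinguishable pain at the target sites. Criterion 3.1.8 reads "Patient average BPI pain score for last 72 hours at specified location is" at least 3. Criterion 3.1.9 accepts painful untreated bone metastases, provided that "the pain from the additional sites must be evaluated as being less intense by at least 2 points on the BPI" relative to the treated sites.

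No section tells the patient or staff to answer item 3 for the treated lesion, asks for one BPI per lesion, or says how one to three targets become one score.

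**The concern.** The quantity intended (pain at the irradiated lesion) and the quantity scored (worst pain anywhere) differ whenever the patient hurts elsewhere. The plan allows this at entry. It sets no limit on non-bone pain and has no rule for pain that appears or worsens elsewhere during follow-up.

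The 2-point margin in 3.1.9 does not clearly protect the response score. It names no BPI item, 3.1.8 uses a 72-hour average, and response uses a 24-hour worst score, so the margin may not hold on the scale that is scored.

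At stake are the category percentages for the first primary objective. If some staff direct the question to the treated site and others do not, at the two participating centres, the percentages also mix two measures.

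**Working it through.** **1. The plan's own figure.** The documents give no figure for the response categories. The one related figure is N = 21 in section 7.2. Inputs: mean change 2, SD 3, two-sided alpha 0.05, power 80%. Effect size d = 2/3 = 0.667. With the Wilcoxon efficiency 3/π = 0.955, the effective n is 21 × 0.955 = 20.05, and noncentral-t power is 0.808; 21 is the smallest N reaching 80%. The figure reproduces. It uses no response category, so this point does not touch it.

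**2. Model.** Let T be worst pain at the treated site and O worst pain elsewhere. Answered as printed, the recorded score is R = max(T, O). Under 6.1.1 with OMED stable: R = 0 is CR; a fall of 2 or more is Partial Response (PR); a rise of 2 or more is Pain Progression (PP); otherwise Stable Pain (SP). Section 6.1.1 gives no number for stable pain; a change under 2 is a convention adopted here. Baseline T is taken as 3 to 10, which applies the threshold of 3.1.8 to the worst-pain scale (an assumption), and scores are capped at 10.

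**3. CR.** R = 0 only if T = 0 and O = 0. Any O of 1 or more blocks CR even when T = 0. Conversely R = 0 implies T = 0, so a false CR cannot arise this way. The error in CR is strictly downward, and no assumption about prevalence is needed.

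**4. Treated site falls to 0, OMED stable.** Scored on the treated site, every pair below would be CR. With a 2-point margin on worst pain, O runs from 1 to T − 2 at baseline, which gives 1 + 2 + … + 8 = 36 pairs.

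| Pain elsewhere | Pairs | CR | PR | SP | PP |
|---|---|---|---|---|---|
| Margin of 2 or more, unchanged | 36 | 0 | 36 | 0 | 0 |
| Same, up 1 | 36 | 0 | 28 | 8 | 0 |
| Same, up 2 | 36 | 0 | 21 | 15 | 0 |
| Same, up 4 | 36 | 0 | 10 | 20 | 6 |
| Margin of 0 or 1, unchanged | 16 | 0 | 0 | 16 | 0 |
| New pain of 1 to 10 at a painless site | 80 | 0 | 36 | 23 | 21 |

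These are counts of possible score pairs, not of patients.

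**5. The favourable direction.** Suppose pain elsewhere exceeds treated-site pain on the worst-pain scale at baseline: O from T + 1 to 10, or 7 + 6 + … + 0 = 28 pairs.
- Pain elsewhere resolves, T unchanged, OMED stable: R falls by O − T, which is 2 or more in 6 + 5 + 4 + 3 + 2 + 1 = 21 of the 28 pairs. These score PR with no benefit at the treated site.
- T rises by 2 while O stays the same, OMED stable: T + 2 stays within 10 in 27 pairs, and R rises by at most 1 in all 27. Progression at the treated site is recorded as SP.

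**6. OMED.** If OMED falls by 25% or more, 6.1.1 scores stable pain as PR. Every SP entry in step 4 then becomes PR; CR stays blocked. If OMED rises by 25% or more, CR and PR are unavailable whatever the pain score, and recorded pain that has not changed scores PP.

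**7. Weight of one patient.** 1/30 = 3.3 percentage points; if only 21 patients were assessed at a visit (an assumption), 1/21 = 4.8. The share with persisting other pain is not given. If it were 20%, 40% or 60% of treated-site complete responders (assumed, with OMED stable), 10 such responders would be recorded as 8, 6 or 4.

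**The case against.** The strongest reply is that the protocol already uses the BPI by site. The printed form supplies neither a 72-hour recall nor a site score, so 3.1.8 and 3.1.9 can be applied only if staff put site-directed questions at screening. With the Study Overview, this suggests that treated-site scoring is meant and that 7.3 and Appendix H fail to carry it through. The response definition is also adopted from a cited consensus guideline, which may name the treated site; that cannot be checked from the documents. Both points stand as limits: the documents do not show that unsited scoring was chosen. But the item that patients complete at follow-up still carries no site and no instruction supplies one.

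The margin in 3.1.9, where it holds on worst pain, means that unchanged pain elsewhere with stable OMED lowers CR to PR and no further. That stands, but it does nothing for CR. The diagram in item 2 can show that the worst pain lies elsewhere, but it gives no treated-site score, and 6.1.1 and 7.3 do not use it.

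A reader might infer that the plan understates response overall. The documents do not support this. Step 5 gives errors in the favourable direction, concurrent chemotherapy is allowed (3.1.11), and a fall in OMED restores PR. Nor can the pair counts be read as expected patient proportions.

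**Conclusion.** The point holds, conditional on item 3 being answered as printed. The CR percentage can then only be biased downward. PR, SP and PP can be misclassified in either direction: new or worse pain elsewhere can hide a treated-site response or produce a false PP. Where other pain is the higher score, its resolution can produce a false PR, and its persistence can mask treated-site progression.

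The size of the bias and the net direction for overall response cannot be computed, because the documents do not give the share of patients with other pain or its course. The consequence is limited: this is a 30-patient single-arm pilot, the percentages are descriptive with no threshold attached, and N = 21 stands. It still matters because the categories serve the first primary objective, and treated-site scores not collected at the time cannot be recovered later.

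The pre/post Wilcoxon comparison may share the problem: 7.3 does not say which BPI item it uses.

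**What to change.** - At baseline and at each BPI administration, add one 0-10 question for each target lesion: worst pain in the last 24 hours at the treated site.
- State in 6.1.1 and 7.3 that the response categories use this score, with a rule for two or three targets (for example, the worst treated site).
- Keep the unmodified BPI item and report the categories from it alongside.
- State in 7.3 which BPI item the Wilcoxon test uses, and report the same test on the treated-site score.
- State, when response is reported, that OMED is whole-body.
- For visits already completed, use the item 2 diagram to flag those where the worst pain is not at a treated site.

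The cost is one to three extra questions per questionnaire at existing visits, matching case report form fields, and a few sentences of text. The added question lies outside the validated form. It also cannot separate opioid use by site: where OMED has risen because of pain elsewhere, it can remove a false PP that came from a recorded rise in pain but cannot restore CR or PR.
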